In use in children this medication is available in liquid form and will be

prepared and dispensed by the UW/AFCH for subjects who are unable to swallow pills or take solid medications.

Patients will undergo a 3-month treatment period followed by a 1-month follow-up period. Visit length and testing is typical for an initial evaluation/consultation in the pediatric ophthalmology clinic. All testing is performed in the pediatric ophthalmology clinics by staff experienced and trained in visual testing of the pediatric population. The PI has 15 years of clinical experience in pediatric ophthalmology alone and is fellowship trained in pediatric ophthalmology, it is well within the ability of most all patients to perform these test within one setting except where noted based on age. In some cases it is expected that tests other than the primary outcome data may not be obtainable in all patients. Patients will be removed from the study if they cannot complete the primary outcome (visual acuity) testing. Other vision testing (color testing, SVEP, Contrast, photography, and OCT) will be requested, but not required to participate in the study. Please see schedule of visits below for detail.

Research Design:

Patients with Oculocutaneous albinism will be recruited ages 3 and up, weight greater than 25 pounds. Entrance into the study is dependent upon clinical evidence of decreased or absent pigmentation in skin, hair, and eyes. No ocular only albinos will be recruited. Additionally, all patients enrolled in the study will be requested but not required to undergo genotyping (TYR and OCA2) gene) of their form of albinism, if not already known. These two types of albinism are the most common, and, for most clinical observers - indistinguishable. However, the presence or absence of TYR theoretically has a direct impact on expected visual response to dopamine replacement. The genotypic form of albinism has no known implications for other aspects of health, clinical care. overall health prognosis or insurability. Indeed, because the genotype has no influence on diagnosis or treatment, it is expected that less than one in ten patients recruited will have been previously tested. Testing will be performed by a certified national clinical lab with validated testing. No "out of pocket" expense for this test will be incurred by the family of the patient. Costs for testing will be covered by funding from the UW Department of Ophthalmology.

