Based on a standard deviation estimate of logMAR from a study on ocular albinism patients (Wildsoet C.F., et al: Investigative Ophthalmology and Visual Science: 2000) of 0.23, a minimum of 44 patients is the required recruitment to find a treatment effect of 0.1 logMAR visual acuity with a paired T-test between

changes due to treatment powered at 80%..Anticipated recruitment would be 50 patients total to allow for possible loss-to-follow-up and sufficient accrual.

If a patient discontinues treatment early, the treatment and the reason will be documented, and they will be asked to still report for their data collection appointments. If data is missing from the treatment phase, that patient will be unable to be used in the final analysis. Hence, we plan to recruit extra patients to ensure full data from at least 44 patients.

As previously mentioned, supportive measures are the only treatment modalities available to albinos, if a standard of care group were used it would be therefore, no treatment. The primary outcome is change from baseline, and since albinism is a chronic condition with no change in vision is the well-established natural history no standard of care group will be necessary – all patients enrolled will receive the standard supportive measures in addition to treatment.

Treatment with Carbidopa in combination with Levodopa inhibits decarboxylation of peripheral Levodopa. Carbidopa does not cross the bloodbrain barrier and does not affect the metabolism of Levodopa within the central nervous system. Since its decarboxylase inhibiting activity is limited to extra cerebral tissues, administration of Carbidopa with Levodopa makes more Levodopa available for transport to the brain. Studies show Carbidopa saturates the bodies peripheral Dopa decarboxylase enzyme at approximately 70 to 100 mg (1mg/kg/day) a day. Patients receiving less than this amount of Carbidopa are more likely to experience nausea and vomiting. This is the basis for the higher dose of 4mg/kg/day of Levodopa treatment in this study, at this dose the minimum amount of Levodopa would be available to the retina (a tissue protected by the blood-brain barrier), as the Carbidopa dose of 1mg/kg/day would reach a peripheral enzyme saturation level. This is the basis for the typical starting dose for treatment of Parkinson's disease, but less than half the typical dose for treatment of DRD in children.

Drug dosing:

Levodopa dosages:

Total daily divided	weight lbs	weight kg

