Risks from testing: Patients will undergo a complete ophthalmic exam twice in three months. Children under 7 have this every 6 months and over 7 yearly. Standard, but more invasive testing procedures include: VEP, photography, and OCT. Visual Evoked Potential (VEP) testing is an electrophysiologic recording of brain wave activity similar to EEG recording that takes 10 minutes while subjects watch a computer screen. This test is performed routinely (30 times/wk) on preverbal patient in the clinic and is very well tolerated. Photography and OCT (a form of photography) requires subjects look into the camera while image is captured -- each image is recorded in less than 5 seconds.

Finally, every safety measure will be put into place to limit breaches of confidentiality. Patient confidentiality has been discussed in several areas of this protocol and include, but are not limited to: genotyping results, pregnancy testing of minors, and clinical documentation of visual performance including photographic information.

Statistical:

The primary analysis will be to look at the paired differences of the changes in logMAR due to 3-month treatment for each subject when compared to baseline. Sample size calculations based on finding a 0.1 logMAR difference in visual acuity at 95% confidence, with a standard deviation of .23, shows a minimum sample size of 44 patients needed to find a significant effect with 80% power. Other investigators have used the .2 logMAR vision improvement as marker of utility of vision improvement.⁶

This study will have an intent to treat goal. Anyone that fits the inclusion criteria for the study regardless of baseline logMAR vision or OCA type will be entered in the study. The goal will be to have 50 patients to ensure at least 44 patients in treatment, after any possible dropouts. Stopping criteria for enrollment will be a total recruitment of 50 patients, additionally after 22 patients (half) complete the course of treatment, the data will be analyzed for potential benefit. If significant results are found, the trial will be concluded.

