Data from 19 completed subjects was analyzed. The standard deviation of differences of logMAR (from baseline to on-treatment) has been estimated to be 0.085. Using a more conservative estimate of 0.1, a one-sample t-test with a significance level of 0.05 and power of 80% would be able to detect a difference of 0.053 when 30 subjects are included in the trial. Hence, 30 subjects will enable us to achieve enough power to confidentially test for changes of 0.1 logMAR.

Data collection:

A physician or clinical technician trained in ophthalmology or

ophthalmologic photography will perform clinical data collection during the clinical visit in a private setting. All procedures will be consented to. Results of research testing (genotyping and pregnancy testing) will be kept in a study chart; results of clinical test will be recorded in the UW clinical chart and study chart. Additionally, all the data collection forms will be coded numerically to keep the data separate from any patient identification.

Genotyping (5cc purple top tube)

All tubes will be labeled with a study patient ID number, drawn at the University Station lab. Upon receipt at the central laboratory (Casey Oregon) the lab coordinator will remove the blood from the tubes and transfer it to the centrifuge for DNA extraction. All DNA samples will be held for only 6 months after completion of the study, in the event the testing would need to be validated, and labeled only with study ID number, a number that cannot be identified with a particular individual by anyone outside of the study clinical center at the UW. Casey eye institute will not be using DNA for any additional purposes.

Urine pregnancy testing will be performed anonymously by the UW lab and resulted to the study coordinator within one hour.

Labeling Procedures

Specimen labels will be provided to the clinic by the Study Coordinating Center. Each set of labels will have a unique *5-digit random specimen identification number* that will be pre-printed on the labels. The date the sample was drawn will be completed by the clinical center at the time the specimen is obtained. No other markings will be placed on the specimen or its container that contain personally identifying information.

All study patient records and data with study patient ID numbers and name codes are stored independent from the data, in a locked office at [name]. The clinic coordinator and PI have access to records.

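### The current text still says 44 patients are needed for 80% power at 0.1 logMAR using SD 0.23, a value the trial's own SD of change rules out; the error is conservative

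*Combined protocol and SAP*

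**What the plan says.** The primary analysis is a within-patient comparison of 3 months with baseline: "The primary analysis will be to look at the paired differences of the changes in logMAR due to 3-month treatment for each subject" (Statistical).

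The sample-size paragraph in Research Design begins "Based on a standard deviation estimate of logMAR from a study on ocular albinism patients" and continues "of 0.23, a minimum of 44 patients is the required recruitment to find a treatment effect of 0.1 logMAR visual acuity", with a paired t-test at 80% power. Recruitment is set at 50 so that at least 44 patients have full data. The Statistical section restates it: "Sample size calculations based on finding a 0.1 logMAR difference in visual acuity at 95% confidence, with a standard deviation of .23", giving 44 patients and 80% power. It also sets an interim analysis after 22 patients, described as half.

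The last paragraph of the Statistical section then gives an estimate from 19 completed subjects: "The standard deviation of differences of logMAR (from baseline to on-treatment) has been estimated to be 0.085". It adopts 0.1 as a more conservative value, finds that 30 subjects can detect 0.053 with 80% power, and concludes that 30 are enough to test for 0.1 logMAR. It does not say that this replaces the 44 and 50 above it.

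On population, Research Design states "No ocular only albinos will be recruited".

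**The concern.** A paired t-test is powered on the SD of within-patient differences. The plan introduces 0.23 only as an SD of logMAR and gives neither a within-patient correlation nor a reason to treat it as an SD of change. When the plan means change, in the re-estimation paragraph, it says so. The source is also described as a study of ocular albinism, while this trial does not recruit patients with ocular albinism only.

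Two things are at stake. The figure of 44 (50 recruited) justifies how many patients, including children from age 3, receive the drug. The 80% also tells readers that the trial is tuned to an effect of about 0.1 logMAR. If the SD of change is much smaller than 0.23, the trial will usually declare significance for effects well below that target, and the two 0.23-based statements do not show this.

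**Working it through.** **Inputs.** Effect 0.1 logMAR, SD 0.23, n = 44, power 80% (Research Design and Statistical). Alpha 0.05, from 95% confidence (Statistical). SD of differences 0.085 from 19 subjects, adopted SD 0.1, n = 30, detectable difference 0.053 (Statistical, last paragraph). Sidedness is not stated.

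**Method.** One-sample t-test on paired differences, using the noncentral t distribution with n − 1 degrees of freedom and noncentrality (effect / SD) × √n.

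**1. Reproduce 44.** With 0.23 entered directly as the SD of differences, two-sided 0.05:
- Noncentrality at n = 44 is (0.1 / 0.23) × √44 = 2.884, and power is 80.5%. At n = 43 power is 79.5%, so 44 is the minimum.
- One-sided 0.05 gives 35, so the plan's figure corresponds to a two-sided test.

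The arithmetic is right. The 0.23 was used as the SD of paired change.

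**2. Reproduce 0.053.** At SD 0.1, n = 30, two-sided 0.05, 80% power is reached at 0.0529. This agrees with the plan.

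**3. Is 0.23 compatible with the trial's data?** With 18 degrees of freedom, the 95% interval for the SD is 0.085 × √(18 / 31.53) to 0.085 × √(18 / 8.23), that is 0.064 to 0.126. If the true SD were 0.23, 18 × 0.085² / 0.23² = 2.46 would be a chi-square value on 18 degrees of freedom. A value that low or lower has probability of about 6 in a million.

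**4. What the design delivers at 0.1 logMAR (two-sided 0.05).**

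| SD of change | n for 80% power | Power, n = 30 | Power, n = 44 | 80% power at, n = 30 | 80% power at, n = 44 |
|---|---|---|---|---|---|
| 0.23 | 44 | 63.4% | 80.5% | 0.122 | 0.099 |
| 0.126 | 15 | 98.7% | 99.9% | 0.067 | 0.054 |
| 0.1 | 10 | 99.96% | >99.9% | 0.053 | 0.043 |
| 0.085 | 8 | >99.9% | >99.9% | 0.045 | 0.037 |

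At the interim size of 22, a nominal two-sided 0.05 test has 49% power for 0.1 logMAR at SD 0.23 and 99% at SD 0.1.

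**5. If 0.23 is a spread of levels (assumption).** With the same level SD at both visits, SD of change = 0.23 × √(2(1 − ρ)), where ρ is the baseline to 3-month correlation. The plan gives no ρ, so these are illustrations:

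| ρ | SD of change | n for 80% power | Power, n = 44 |
|---|---|---|---|
| 0 | 0.325 | 85 | 51% |
| 0.5 | 0.23 | 44 | 80% |
| 0.75 | 0.163 | 23 | 98% |
| 0.9 | 0.103 | 11 | >99.9% |

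On this reading, the plan's 44 holds only at ρ = 0.5, which it neither states nor supports.

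**The case against.** The strongest reply is that the plan has already dealt with this. The re-estimation paragraph uses the right quantity, from the trial's own patients, in a calculation that reproduces, and it openly states that 30 subjects detect 0.053. A power statement is also conditional on its assumed SD. A planning value that later proves too large is cautious, and the arithmetic behind 44 is sound. All of this stands, and it limits the point to two live statements that were not brought into line. It does not remove the point, because both sections still present 44 as the required minimum and nothing marks them as superseded.

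A reader might go further in three ways that the documents do not support:

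- **That 0.23 is certainly an SD of levels.** The contrast in wording makes this a strong inference, but the plan never says so and the cited study is not available here. The correlation of 0.50 above depends on it. So does the figure of about 0.93 obtained from 1 − 0.085² / (2 × 0.23²), which also needs 0.23 to be this trial's level SD at both visits.
- **That the trial is underpowered.** On its own SD of change it has ample power for 0.1 logMAR at either 30 or 44. The 51% in step 5 needs zero correlation between visits, an illustrative assumption.
- **That the plan conceals its sensitivity to small effects.** The 0.053 is disclosed for 30 subjects. Only the 0.23-based statements fail to convey it.

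The mismatch with ocular albinism is secondary now that the plan has an SD from its own patients.

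**Conclusion.** The point holds in a limited form. The statement that 44 patients are required for 80% power at 0.1 logMAR does not describe this paired design, because the trial's own SD of change excludes 0.23 whatever that figure measured. The error is conservative: at SD 0.1 the 0.1 logMAR target needs 10 patients. With 44 patients, power is above 99.9% and 80% power is already reached at 0.043 logMAR, less than half the target.

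This rests on a two-sided 0.05 test, approximately normal differences, the 19 completed subjects being representative of the rest, and the on-treatment measurement being the 3-month one. It does not rest on 0.23 being a spread of levels. The stated objective is not at risk. What needs correcting is the stated justification for the number treated and the account of what effect the trial can detect.

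**What to change.** In the sample-size paragraph of Research Design and in the Statistical section:

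1. Withdraw the 0.23-based statement of 44 required and 80% power, or mark it as superseded by the calculation from the 19 completed subjects.
2. Base the power statement on the SD of within-patient change: 0.1 as already adopted, optionally with 0.126 as a sensitivity value, at which 30 patients still give about 98.7% power for 0.1 logMAR. State that the test is two-sided.
3. Say which enrolment number governs, and give its power and detectable difference. At SD 0.1 these are 99.96% and 0.053 for 30 evaluable patients, or above 99.9% and 0.043 for 44.
4. Reconcile 44 evaluable, 50 recruited and the interim look at 22, defined as half of 44, with the 30 in the last paragraph of the Statistical section.

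The cost is wording only, with no added patients, visits or tests. The one consequence is that the 0.23 calculation can no longer be cited to justify 44 or 50; if either number is kept, it needs another stated reason.

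### The plan drops patients with missing treatment-phase data and plans no analysis of them, so the primary result is an observed-case estimate despite the stated intent-to-treat goal

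*Combined protocol and SAP*

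**What the plan says.** The rule is in the Research Design section, in the paragraph on early discontinuation: "If data is missing from the treatment phase, that patient will be unable to be used in the final analysis". The remedy follows at once: "Hence, we plan to recruit extra patients to ensure full data from at least 44 patients". The same paragraph limits loss. For a patient who stops early, "the treatment and the reason will be documented", and "they will be asked to still report for their data collection appointments".

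The Statistical section says "This study will have an intent to treat goal". The sentence after it concerns entry only: eligible patients are enrolled whatever their starting acuity or type of albinism. The analysis is defined as "The primary analysis will be to look at the paired differences of the changes in logMAR due to 3-month treatment for each subject", set against baseline.

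The testing paragraph under Study Objectives adds "Patients will be removed from the study if they cannot complete the primary outcome (visual acuity) testing", without saying whether this applies before or after the first dose. The other vision tests "will be requested, but not required to participate in the study".

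Data/Safety monitoring asks withdrawn patients back for a visit after the taper, but does not say whether acuity from that visit enters any analysis. The documents contain no imputation rule, no missing-data assumption and no sensitivity analysis.

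**The concern.** A paired change from baseline to 3 months needs both acuities. Under the exclusion rule, a treated patient without a 3-month acuity leaves the analysis and does not reappear in any other. Because the rule says data rather than acuity, a literal reading could exclude more. Only acuity is mandatory, so the sensible reading is acuity at baseline and 3 months, but the plan should say so.

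Extra recruitment restores precision. It does not make the patients with data representative of those treated. The documents show routes by which loss could be related to outcome: withdrawal for adverse events judged too severe (Risks), and families who may have to pay for the drug (Research Design). With no control arm, nothing offsets such selection. If the lost patients did less well than the rest, the reported gain is too large, and a reader who sees the intent-to-treat label would not expect that.

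**Working it through.** **1. The plan's own figures.** For a two-sided paired t-test at 0.05 with a difference of 0.1 logMAR and SD 0.23 (Research Design and Statistical), 44 patients give power 0.805, so the stated minimum reproduces. Recruiting 50 implies an allowance of 6/50 = 12%, since 44/(1 − 0.12) = 50. For 30 subjects with SD 0.1 (Statistical, the re-estimate from 19 completed subjects), the detectable difference is 0.0529, matching the stated 0.053. With only 26 of 30 observed it is 0.057, and power for 0.1 logMAR stays above 99%. Power is not the problem.

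**2. Method for the illustration.** The number lost and the changes of lost patients are assumptions, and improvement is counted as positive. With n observed (mean m, SD s), k lost patients set to change d, and N = n + k:

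- M = (n·m + k·d)/N
- SD² = [(n − 1)s² + n(m − M)² + k(d − M)²]/(N − 1)
- two-sided t-test of M/(SD/√N) on N − 1 df

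**3. 50 treated, 6 lost, observed mean 0.100, SD 0.23.** Observed cases: SE = 0.23/√44 = 0.0347, t = 2.88, p = 0.0061.

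At d = 0: M = (44 × 0.100)/50 = 0.088; SD² = [43 × 0.0529 + 44 × 0.012² + 6 × 0.088²]/49 = 0.0475; SD = 0.218; p = 0.0063.

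| Change in lost patients | All-treated mean | p |
|---|---|---|
| 0 | 0.088 | 0.0063 |
| −0.10 | 0.076 | 0.021 |
| −0.20 | 0.064 | 0.062 (95% CI −0.003 to 0.131) |

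The lower limit reaches 0 at d = −0.179.

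**4. 30 treated, 4 lost, observed mean 0.100, SD 0.1.** The all-treated mean is 0.087, 0.073 and 0.060 at 0, −0.10 and −0.20 (p = 0.025 at −0.20). The tipping value is −0.235.

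**5. 30 treated, observed mean 0.053, SD 0.1.** With 4 lost at zero change, the mean is 0.046 and p moves from 0.0122 to 0.0126. With lost patients at −0.10:

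| Lost | Observed | All-treated mean | p |
|---|---|---|---|
| 1 | 29 | 0.048 | 0.016 |
| 2 | 28 | 0.043 | 0.032 |
| 3 | 27 | 0.038 | 0.060 |
| 4 | 26 | 0.033 | 0.11 |

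For 3 lost: M = (27 × 0.053 − 3 × 0.10)/30 = 0.0377. With 4 lost, the tipping value is −0.062.

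**6. A limit of this method.** Giving every lost patient the same value leaves out their own scatter and understates the SD. Adding k·s² to the bracket in SD², so that lost patients vary as much as observed ones, moves the three tipping values from −0.179, −0.235 and −0.062 to about −0.154, −0.227 and −0.048. The constant-fill values are therefore somewhat too reassuring.

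**The case against.** The strongest reply is that the only assumption the documents support hardly matters. Research Design takes stable vision as the natural history of albinism. Setting lost patients to zero change lowers the estimate by 0.007 to 0.013 logMAR (4 or 6 lost) and barely moves p. Significance goes only if lost patients worsen, and no section suggests that treatment or dropout worsens acuity. The fragile case needs three assumptions together: an observed mean near 0.053, at least 3 of 30 lost, and each of them 0.10 worse. The plan also works to keep patients in follow-up, and it states its exclusion openly. All of this stands, and it limits the weight of the point. It does not supply the missing analysis or justify the label.

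A reader might also infer that the removal sentence under Study Objectives drops treated patients. The documents do not support that. Its timing is not stated, and the surrounding text is about which tests patients of a given age can perform, so a check before dosing is at least as natural a reading.

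Nor is this an on-treatment analysis, as a reader might suppose. Early stoppers who attend and have a 3-month acuity can be included.

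**Conclusion.** The point holds, resting on the exclusion rule in Research Design and the intent-to-treat wording in the Statistical section. The primary result will be an observed-case estimate, and no planned analysis shows how far it depends on the patients left out.

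The size is conditional. An observed gain of 0.1 logMAR is fairly robust to the losses illustrated. A gain near 0.053, which the re-estimate says 30 subjects can detect, is not robust once 3 or more lost patients worsen by 0.10. A reader might conclude that the reported gain will be inflated. The documents do not show that: they give no dropout rate and no profile of lost patients, so neither direction nor amount is known. This should be corrected, but it does not make the estimate unusable.

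**What to change.** 1. Replace the exclusion sentence in Research Design. The primary analysis should include every treated patient with a baseline and a 3-month visual acuity, regardless of adherence, early stopping or other missing tests, and be labelled observed-case. State in the testing paragraph under Study Objectives that a patient who has been dosed and cannot complete 3-month acuity testing counts as treated with a missing outcome.
2. Prespecify one sensitivity analysis of all treated patients with a baseline acuity. Set missing 3-month changes to 0, the plan's own premise of stable vision, and then to a range of worse values labelled as assumptions. Report the value at which the 95% interval first includes 0. Use multiple imputation with a shift, or state that single constants understate the SD and make the tipping value look too reassuring.
3. Use the intent-to-treat label only for the all-treated estimate. Report the number without a 3-month acuity and the reasons; the plan already documents reasons for stopping treatment early.

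The cost is wording in three sections and one extra analysis, with no added visits or patients. The downside is a slightly less favourable all-treated estimate, about 0.007 to 0.013 logMAR lower at zero change in the illustrations with 4 or 6 lost, and the chance that a modest significant effect is shown to be fragile.

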Information collected from the record will include patient's age, sex, race, genotype of albinism (if known) and the outcome measures listed above, results of clinical testing will be recorded in the clinic chart in addition to a study chart and research will only be recorded in the study chart. Research tests including results of genotyping will not be shared with subjects or family. For females who have had a menstrual cycle, positive results of screening pregnancy tests will be given to the subject in private, not shared with the parent.

Patients include OCA1a patients, OCA1b, OCA2, and unclassified OCA. OCA1a patients clinically are known to have the worst vision, and physiologically have the lowest (or absent) levels of tyrosinase function (Dopamine Production). All patients will be treated with Levodopa/carbidopa 4mg/kg/day in three divided doses (Dose determination outlined below). Patients and their families will be asked to submit the costs of medication to their insurance companies or cover the costs themselves, if this cost is not covered by their insurance. Per the UW Pharmacy, the pricing for 30 Carbidopa/Levodopa tablets is \$27.81, the oral suspension would cost \$32.32 for 100 mL. Subjects under 135 pounds would require an oral suspension provided by the UW pharmacy, in order to control the appropriate dose. This formulation has been adapted from The Hospital for Sick Children (University of Toronto). The ingredients for this formulation consist of: Carbidopa 25 mg/Levodopa 100 mg tablets (quantity = 5), Ora-Plus 50 mL, and Ora-Sweet 50 mL. Subjects over 135 pounds could obtain the drug at an outside pharmacy. Treatment will continue for 3 months followed by a six day taper reduction in dose (3 days at twice per day and 3 days at once per day), as a rapid reduction in dosage can be associated with fever, stiff muscles, confusion, abnormal thinking, fast or irregular heartbeat, and sweating. Side effects reported in adults with Parkinson's disease on Levodopa/carbidopa will be monitored (see schedule) and include nausea, headache, mood changes, insomnia, nightmares, dizziness, tiredness, leg pain, tinnitus and emesis. (These have not been reported in studies of Levodopa/Carbidopa in children)

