tid (mg)		
60	25-33	11-15
75	34-47	>15-21
100	48-60	>21-27
125	61-74	>27-34
150	75-89	>34-40
200	90-117	>40-53
250	118-134	>53-61
300	135-159	>61-73
4mg/kg/day	>160	>73

Confidentiality:

A physician or clinical technician trained in ophthalmology or

ophthalmologic photography will perform data collection during the clinical visit in a private setting. All procedures will be consented to.

All records, including the data collection forms, will be coded numerically to keep the data separate from any patient identification. A log that includes the subject identification and assigned code will be stored independently from the data. Data will be stored in a locked office or on an isolated hard-drive desk top computer which is password protected and can only be accessed by the PI. The hard drive of the PI is backed-up hourly. In addition, the study coordinator will have access to the paper charts used to monitor the treatment and adverse events. No study data or subject logs will be stored on portable laptop computers. Photos will not be stored with study data, only reviewed from the medical record.

Study Schedule:

I -- Pretreatment

- 1 Informed Consent/Assent
- 2 Blood pressure, heart rate, weight.

Elevated blood pressure will need to be under control by the primary care provider prior to entry into the study.

- 3 Ophthalmic Exam complete with cyclopentolate 1% dilation (standard dilation drops used in the pediatric clinic in children over 20 pounds)
 - a. Snellen visual acuity or HOTV
- b. Color vision Farnsworth 15 or 100 hue, patients old enough to participate (estimated 6 years old and up)
- c. Sweep visual evoked potential (VEP) (standard test in clinical setting -10 min test patients "watch a computer monitor" while recordings are made of vision response)
 - d. Contrast Sensitivity (5 min test on contrast board)
 - e. Color photography (Only performed If not current within the last 3 yrs) (all photos and Optical Coherence Tomography (OCT) take about 10mins)

predilation iris and full face postdilation fundus postdilation OCT

- 4 Optional Blood draw for genetic subtype analysis if unknown (5ml purple tube).
 - 5 Females who are pregnant, lactating, or intending to become pregnant within the next 12 weeks. A negative urine pregnancy test will be required for all females who have had a menstrual cycle.
- II 1 day, 1 week and 1-month treatment phone call check compliance, and adverse events.

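### The pound and kilogram columns of the levodopa table give different daily doses at 47, 60, 89 and 117 lb, and no governing unit is stated

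*Combined protocol and SAP*

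**What the plan says.** The treatment paragraph of the protocol, after the recruitment text, sets the nominal dose and sends the reader to the table: "All patients will be treated with Levodopa/carbidopa 4mg/kg/day in three divided doses (Dose determination outlined below". The Pharmacology section repeats 4 mg/kg/day of levodopa.

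The table under Drug dosing is headed "Total daily divided weight lbs weight kg". Each row carries one daily dose in mg, one pound band and one kilogram band. Consecutive rows include "100 48-60 >21-27", "125 61-74 >27-34", "150 75-89 >34-40" and "200 90-117 >40-53". The last row is "4mg/kg/day >160 >73", and the row above it ends at 159 lb and 73 kg.

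The pound bands are whole-number ranges. The kilogram bands are contiguous, each opening just above the limit of the one before. The documents do not say which column governs, in what unit the patient is weighed, or how a converted weight is rounded. The pretreatment list in the Study Schedule asks only for weight.

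**The concern.** The table is the working dose rule, so either column should select the same row for a given patient. At four whole-pound weights it does not. Staff have reason to use both units: eligibility and the choice between suspension and tablets are set in pounds, while the nominal dose is per kilogram.

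At stake is consistency of dosing. Two patients of the same weight could be given daily doses one band apart, and both doses would comply with the protocol as written.

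**Working it through.** **Inputs.** The pound and kilogram limits are from the table under Drug dosing. The nominal 4 mg/kg/day is from the treatment paragraph and Pharmacology. The 30 subjects and 19 completed subjects are from the last paragraph of the Statistical section. The conversion is the standard 1 lb = 0.45359237 kg.

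**Step 1: how the kilogram limits arise.** Converting each pound upper limit gives:

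| Upper limit, lb | Exact kg | Printed kg |
|---|---|---|
| 33 | 14.97 | 15 |
| 47 | 21.32 | 21 |
| 60 | 27.22 | 27 |
| 74 | 33.57 | 34 |
| 89 | 40.37 | 40 |
| 117 | 53.07 | 53 |
| 134 | 60.78 | 61 |
| 159 | 72.12 | 73 |

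Seven of the eight printed limits equal the pound limit rounded to whole kilograms; 159 lb is the exception. At 47, 60, 89 and 117 lb the rounding went down. The heaviest patient in each of those pound bands is therefore already in the next kilogram band.

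**Step 2: look up both columns.** For each whole pound from 25 to 180, the pound bands were read as closed ranges and each kilogram band as above its lower figure up to and including its upper figure. With unrounded conversion, these five weights disagree and no others:

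| lb | kg | Pound column | Kilogram column | Ratio |
|---|---|---|---|---|
| 47 | 21.32 | 75 mg (3.52 mg/kg) | 100 mg (4.69 mg/kg) | 100/75 = 1.33 |
| 60 | 27.22 | 100 mg (3.67) | 125 mg (4.59) | 125/100 = 1.25 |
| 89 | 40.37 | 150 mg (3.72) | 200 mg (4.95) | 200/150 = 1.33 |
| 117 | 53.07 | 200 mg (3.77) | 250 mg (4.71) | 250/200 = 1.25 |
| 160 | 72.57 | no row | 300 mg (4.13) | not defined |

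Dividing by 2.2, 2.2046 or 2.205 gives the same five weights.

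**Step 3: does a rounding rule rescue the table?**
- Patient weight rounded to whole kg: the four conflicts vanish, but new ones appear at 34 lb (75 vs 60 mg), 75 and 76 lb (150 vs 125 mg), 135 lb (300 vs 250 mg), and 161 and 162 lb (4 mg/kg vs 300 mg).
- Rounded to 0.1 kg: all four remain, and 75 and 161 lb are added.
- Truncated to whole kg: the conflicts move to other weights, including 48, 61, 90 and 118 lb.
- The gap at 160 lb remains under every convention.

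**Step 4: how wide the overlaps are.** Converted back, 21, 27, 40 and 53 kg are 46.297, 59.525, 88.185 and 116.845 lb. The overlaps are 47 - 46.297 = 0.703, 60 - 59.525 = 0.475, 89 - 88.185 = 0.815 and 117 - 116.845 = 0.155 lb. Their sum is about 2.15 lb.

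**Step 5: how many patients.** Assume weights uniform over 25-160 lb; the documents give no weight distribution.
- Continuous weights: p = 2.15/135 = 0.0159. Expected 30 × 0.0159 = 0.48; chance of at least one 1 - (1 - 0.0159)^30 = 0.38.
- Whole-pound weights: p = 4/136 = 0.0294. Expected 30 × 0.0294 = 0.88; chance 1 - (1 - 0.0294)^30 = 0.59.
- If 30 - 19 = 11 patients remain to be dosed (an assumption): 11 × 0.0159 = 0.17 and 1 - (1 - 0.0159)^11 = 0.16 with continuous weights; 11 × 0.0294 = 0.32 and 1 - (1 - 0.0294)^11 = 0.28 with whole pounds.

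**The case against.** The strongest reply is that this is a rounding slip and not a pair of rival dose rules. That describes well how the limits arose, but it does not cure the table, because rounding patient weights in the same way only creates conflicts elsewhere.

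A second reply is that the doses in dispute lie within the table's own spread. A 25-33% difference is one band step; in the pound column alone, 89 lb gets 150 mg and 90 lb gets 200 mg. That column already runs from 3.52 mg/kg at 47 lb to 5.29 mg/kg at 25 lb (60 mg / 11.34 kg). This stands, and it limits the consequence. A reader might infer that exposure and tolerability can no longer be tied to a defined dose. The documents do not support that: each patient's assigned dose in mg is definite and can be recorded, and no exposure-response analysis is planned.

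Third, all four double-dose weights are below 135 lb, where the suspension comes from one university pharmacy. Inconsistent dosing would need different units for different patients within that pharmacy, and nothing shows that this happened. The protocol's other weight thresholds are in pounds. This lowers the likelihood but does not settle which column governs.

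Fourth, the 160 lb gap is small. The kilogram row's 300 mg is about 3% above the 290.3 mg implied by 4 mg/kg × 72.57 kg. This stands.

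**Conclusion.** The columns contradict each other and should be corrected. With unrounded conversion, a patient of 47, 60, 89 or 117 lb has two daily doses under the same table, the kilogram one 25-33% higher. No rounding convention examined reconciles the columns. The gap at 160 lb is a minor addition.

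The reach is small. Each overlap is under 1 lb wide. On the uniform-weight assumption, about 0.5 to 0.9 of 30 patients are affected, with a 38% to 59% chance of at least one, depending on whether weights are continuous or in whole pounds. The figures fall if many adults weigh more than 160 lb or if only patients still to be dosed are counted.

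A reader might take 59% as the chance that someone is dosed inconsistently. It is only the chance that someone lands on an ambiguous weight. Nor do the documents show that those affected would mostly be children: adults are eligible with no upper weight limit, and no age or weight distribution is given. The sample size and the primary analysis, a paired change in logMAR, are unaffected.

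**What to change.** The sponsor and pharmacy should reconcile the two columns. They should name one governing unit with contiguous limits, derive the other column by conversion with a stated rounding rule, and make sure 160 lb falls in a row. For patients already treated, they should record the unit used and the daily dose assigned in mg. Which limits and doses are right is for them to decide; no view is taken here.

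The cost is one table correction in an amendment, a notice to the pharmacy and a short check of existing dosing records. The sample size and analysis plan need no change.
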